#### 5 STUDY EVALUATIONS AND MEASUREMENTS

#### 5.1 Screening and Monitoring Evaluations and Measurements

#### 5.1.1 Medical Record Review

Diagnosis of venous pulsatile tinnitus

Inclusion/Exclusion criteria

Year of Birth

Time since diagnosis (chronicity of current disease)

#### 5.1.2 Physical Examination

- Date of birth
- Gender
- Race

# 5.2 Efficacy Evaluations

#### 5.2.1 Diagnostic Tests, Scales, Measures, etc.

- Primary endpoint: symptom relief
  - Tinnitus aural intensity scale before and after collar administration at each visit and once daily for with collar and without collar intensity
- Secondary endpoint: QOL Impact
  - Tinnitus Handicap Index (Once at beginning of study, once at end)
  - Patient Reported Outcome Measurement Information System (PROMIS) scales in depression, anxiety, physical function, and satisfaction
- Secondary endpoint: Temporality
  - Aural intensity scale submissions will be plotted and compared over time course of study
- Secondary endpoint: Homes vs. clinic use
  - Supervised tinnitus intensity scale measurements will be compared to at home measurements to evaluate if perception of symptomatic intensity varies with environment

# 5.3 Safety Evaluation

Example: Subject safety will be monitored by observation and intervention of adverse events during the physician-supervised fitting period at the beginning of the study and by education of the participants to discontinue use of the collar with any significant change in physical well-being or onset of new symptoms and immediate reporting of that occurrence to the PI and Faculty Advisor through the REDCAP link.

#### **6 STATISTICAL CONSIDERATIONS**

# 6.1 Primary Endpoint

The primary efficacy endpoint will be the change in tinnitus intensity with and without the collar averaged within participants for each completion and across participants the study and

#### 6.2 Secondary Endpoints

Secondary endpoints will include the following:

- The change in participant quality of life
- The effect of time on symptomatic relief
- The effect of medical supervision on symptomatic relief
- Adverse events (none are expected; however, the unlikely occurrence will be tabulated or a lack thereof shall be reported)

# 6.3 Statistical Methods

#### 6.3.1 Baseline Data

Baseline and demographic characteristics will be summarized by standard descriptive summaries (e.g. means and standard deviations for continuous variables such as age and percentages for categorical variables such as gender).

#### 6.3.2 Efficacy Analysis

The primary analysis will be based on an intention to treat approach and will include all subjects who complete the study.

The primary efficacy endpoint will be the change in tinnitus intensity with and without the collar, averaged within and across each patient's completion of the tinnitus scales. This means that there will be 16 paired collar and no collar measurements per patient, one at each clinic visit and one each day during the 14 day intervening period. The significance of this change will be evaluated using a unidirectional t-test.

Secondary endpoints will include the following:

- Temporality of symptom relief
  - Subjects with and without collar scores will be averaged for each day of the study, ANOVA testing will evaluate for the presence of a significant time component.
- Supervised vs. unsupervised use
  - The mean relief recorded at the first and second visit will be averaged and compared avross patients with the mean relief recorded during at home use using a bidirectional t test.
- QOL impacts
  - Evaluated for each scale using bidirectional t test

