Study Phases Enrollment Study Treatment Follow-Up	
 
Participants meeting inclusion/exclusion criteria at UNC
 
Meadowmont will be invited to participate. Those who consent will be fitted with the collar. Then, the at home treatment phase will begin where they report on collar efficacy. Finally, a follow up visit will be conducted to complete exit surveys.
 
	
Efficacy Evaluations	Significant improvement in tinnitus symptoms while wearing collar.	
Safety Evaluations	At intiial visit, team clinician will supervise collar fitting and evaluate for significant pain, discomfort, or adverse effect which will halt participation for that participant and be recorded. During at home study phase, participants will report any adverse effects with their daily recording of symptomatic efficacy.	
Statistical And Analytic Plan	One sided t test on tinnitus intensity while wearing collar vs. while not wearing collar will evaluate primary endpoint of collar relief efficacy. ANOVA analysis of intensity differences will elucidate effect of time, if any. One sided t test will evaluate secondary endpoints of quality of life	
DATA AND SAFETY MONITORING PLAN	Faculty mentor [name] is monitoring all safety related aspects. These include the evaluation of the initial collar fit, collar use education, and reporting of adverse events during at home period.	

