#### 3.1.2 First Visit: Consent, Fitting, Education, Evaluation, Scales

During the first visit, potential participants identified through screening will be invited by a member of the study team to participate. If they agree, they will fill out consent forms, demographics, and preliminary QOL scales through REDCAP, as well as a baseline tinnitus intensity scale. At this point, a clinicial research team member not associated with their care will supervise fitting of the collar. The patient will be monitored for 10 minutes for adverse effects, then asked to complete the scale once more. Lastly, the patient will be educated on fitting and use of the collar, specifically not to use for more than 4 hours daily nor while sleeping, given the collar with its packaging and its instructions, and sent home for home use.

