# 3.2.2 Total Number of Study Sites/Total Number of Subjects Projected

The study will be conducted at approximately 1 investigative site in the United States. This site is the UNC Meadowmont ENT outpatient clinic.

Recruitment will stop when approximately 20 subjects are recruited. It is expected that approximately 22 subjects will be enrolled to produce 20 evaluable subjects.

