# 3.3.2 Subject Exclusion Criteria

- Increased presence of acid in the body or excessive blood alkalinity
- Open head injury (including in or around the eye) within the past six months
- Pseudotumor cerebri (false brain tumor)
- Presence of brain or spinal shunt
- Known seizure disorder
- Known airway obstruction
- Increased likelihood of blood clotting (coagulation)

- age <18
- unable to provide written consent,
- history of neurological deficits,
- previous cerebral infarction (blockage or narrowing in the arteries supplying blood and oxygen to the brain)
- severe head trauma
- medical contraindications to restriction of blood outflow via the internal jugular veins
- glaucoma (narrow angle or normal tension increased pressure in the eyes),
- hydrocephalus (increased fluid on the brain)
- recent penetrating brain trauma (within 6 months),
- known carotid hypersensitivity
- known increased intracranial pressure
- idiopathic intracranial hypertension
- known intracranial vascular malformation (e.g. aneurysm, arteriovenous malformation, cavernoma)
- central vein thrombosis
- not tolerating initial fitting of collar.
- Known pregnancy (this is not a direct contraindication but is being made out of an abundance of caution)
- Inability to speak or comprehend English (this pilot study does not have funding for translators)

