# 4.2 Subject Completion/Withdrawal

Example: Subjects may withdraw from the study at any time without prejudice to their care. They may also be discontinued from the study at the discretion of the Investigator for lack of adherence to study treatment or visit schedules, development of exclusion criteria, or adverse events The Investigator or the Faculty Advisor may also withdraw subjects who violate the study plan, or to protect the subject for reasons of safety or for administrative reasons. It will be documented whether or not each subject completes the clinical study. If the Faculty Advisor becomes aware of any serious, related adverse events after the subject completes or withdraws from the study, they will be recorded in the source documents and on the CRF.

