#### 4.2.1 Early Termination Study Visit

Subjects who withdraw from the study will have all records deleted from the REDCAP database except for adverse events, which will be reported by the Faculty Advisor to the IRB.

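### The primary analysis is called intention to treat but counts completers only, and withdrawn participants' ratings are deleted, so the loss cannot be repaired or examined later

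*Combined protocol and SAP*

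**What the plan says.** Section 6.3.2 defines the primary analysis set in one sentence: "The primary analysis will be based on an intention to treat approach and will include all subjects who complete the study". It does not define completion. Section 6.1 describes the endpoint as "averaged within participants for each completion and across participants". That can be read as covering missed daily entries, but not people outside the set. No missing-data method or sensitivity analysis for leavers is given.

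Section 4.2.1 adds: "Subjects who withdraw from the study will have all records deleted from the REDCAP database except for adverse events". Under section 9.2 all data are collected and stored in REDCap.

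There are several ways out of the study. Participants may withdraw by choice. Under section 4.2 they may be "discontinued from the study at the discretion of the Investigator for lack of adherence to study treatment or visit schedules", or for adverse events. The Protocol Synopsis (Safety Evaluations) provides that at the first visit there is evaluation for "significant pain, discomfort, or adverse effect which will halt participation for that participant and be recorded". Section 3.3.2 lists "not tolerating initial fitting of collar" as an exclusion, although sections 3.1.2 and 4.1.1 place the fitting after consent.

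Ratings start at Visit 1, with a baseline score and then, per section 3.1.2, "The patient will be monitored for 10 minutes for adverse effects, then asked to complete the scale once more". They continue daily for 14 days and end at Visit 2, giving 16 pairs in all. On attrition, section 3.2.2 says: "It is expected that approximately 22 subjects will be enrolled to produce 20 evaluable subjects". By contrast, the safety set in section 6.3.3 takes in everyone who entered at Visit 1.

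**The concern.** The label and the definition contradict each other. A reader who sees the label will take it that everyone enrolled was counted.

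A wrongly named analysis set can usually be put right at analysis. Here it cannot, because the deletion rule removes the data that a correct analysis would need.

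The exits are plausibly related to the outcome. The study is unblinded and single-arm, and the collar is worn as needed. Someone who gets little relief has little reason to wear it, may be discontinued for non-adherence, and then drops out of the efficacy result. If so, the completers' mean overstates relief. The documents give no figures on leavers' relief, so this is plausible rather than established, and the opposite could occur. Once the pairs are gone, nobody can compare leavers' ratings with completers'. Section 2 intends the result to support a multicentre grant application.

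Two related points are undefined: whether deletion under 4.2.1 covers people discontinued by the investigator under 4.2, and how people who consent but do not tolerate the fitting are counted.

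**Working it through.** **What is lost.** Both Visit 1 ratings make one pair, and each home day can add one. Someone who leaves after the Visit 1 ratings and before Visit 2 has 1 to 15 pairs. Someone halted during fitting may have none.

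**Attrition in the plan.** Section 3.2.2 implies a loss of 2/22 = 9.1%. It does not say why the two are not evaluable; if they fail the fitting, few or no pairs are lost.

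**Simple arithmetic.** Suppose completers average 1 point of relief. The mean over all enrolled is then (20 × 1 + 2 × leavers' mean)/22:
- leavers at 0.5: 21/22 = 0.95, overstated by 0.05
- leavers at 0: 20/22 = 0.91, overstated by 0.09
- leavers at −1: 18/22 = 0.82, overstated by 0.18
- leavers at 1.5: 23/22 = 1.05, understated by 0.05

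**Effect on the test.** Simulation with 400,000 replicates. Assumptions: 22 enrolled; participant means normal with true mean 0 and SD 2 (the SD in section 6.4, applied here to participants' mean relief); one-sided t-test at 5%; log-odds of leaving = a − b × (relief/SD), with a set so that 9.1% leave on average. The standard error at n = 20 is 2/√20 = 0.447.

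| Dropout slope b | Bias of completers' mean | One-sided rejection |
|---|---|---|
| −0.5 (better responders leave) | −0.09 | 3.3% |
| 0 (unrelated) | 0.00 | 5.0% |
| 0.5 | +0.09 | 7.3% |
| 1 | +0.17 | 10% |
| Extreme: exactly the two lowest leave | +0.34 | 23% |

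The upward biases at slopes 0.5 and 1 are 0.09/0.447 = 0.2 and 0.17/0.447 = 0.4 of a standard error. At SD 1 the biases halve and the rejection rates are unchanged.

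**What the repair achieves.** If a leaver's pairs represent their full course, using every pair restores a bias of 0.00 and 5% rejection. They may not, because the first pair is taken in clinic. Assume clinic relief is 1 point above home relief. With 2 clinic and 14 home pairs averaging 0, home sits at −2/16 = −0.125 and clinic at +0.875. The residual bias is the leaver's excess × 2/22:
- Visit 1 only: 0.875 × 2/22 = +0.08; simulated rejection 7.1% (9% to 10% at SD 1)
- Visit 1 plus 3 home days: (0.875 − 0.375)/4 = 0.125, × 2/22 = +0.01; 5.3%
- Visit 1 plus 7 home days: (0.875 − 0.875)/8 = 0; 5.0%
- exits spread evenly over 1 to 15 pairs: +0.01; 5.2%

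**The case against.** The strongest reply has four parts.

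1. *The restriction to completers is visible in the same sentence as the label.* In a study without randomisation, this could be seen as a misnomer cured by one word. That is fair for the label alone. It does not touch the deletion rule, which is what makes the matter irreversible.

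2. *Not every leaver has a pair.* This stands. Someone halted at the fitting may have none, and a home day without collar use may give no true with-collar rating. The proposed set would not bring in people without a pair; it can only report their number.

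3. *A check survives, because section 4.2 requires completion status to be documented.* If that record escapes deletion, the result can be bounded. The bound is too wide to help. On a 1–10 scale relief runs from −9 to +9, so with completers at 1 point and two leavers the overall mean lies between (20 − 18)/22 = 0.09 and (20 + 18)/22 = 1.73. It does not show whether leavers had less relief.

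4. *The expected bias is small, its direction is unknown, and the remedy is not uniformly better.* This also stands. At slopes 0.5 to 1 the bias is 0.09 to 0.17 against the 1-point minimum effect in section 6.4. If leavers have only the Visit 1 pair and clinic relief runs 1 point higher, the repaired set (+0.08, 7.1%) is little better than completers at slope 0.5 and worse than completers at slope 0. The case for the repair is that it matches the plan's own label and keeps the data needed to see which situation applies.

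**Conclusion.** The concern holds. The primary set is completers under an intention-to-treat label, and section 4.2.1 erases the efficacy ratings of those who withdraw. This is an error in the plan as written, since no other section retains the ratings or provides for leavers.

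At the planned loss of 2 in 22, the likely distortion is small to moderate if poor responders leave, nil if leaving is unrelated to relief, and downward if better responders leave. The 23% rejection rate is an extreme case and not an expectation. All these figures rest on the assumed dropout slopes, normal participant means and the SD; the documents fix none of the three for leavers. The priority is high because the deletion cannot be undone, so the rule has to change before the first withdrawal.

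**What to change.** - **Section 6.3.2:** define the primary set as every consented participant with at least one collar/no-collar pair, Visit 1 included, using all pairs up to exit whatever the completion or adherence status. Define completion, and report completers under that name as a sensitivity analysis.
- **Section 4.2.1:** keep data collected before withdrawal unless the participant asks for deletion, as far as consent allows. State whether the rule covers people discontinued by the investigator. Make it consistent with the safety set in 6.3.3: adverse events are already kept, but a withdrawn person without one could vanish from the denominator.
- **Reporting:** give numbers and reasons for fitting intolerance, withdrawal and discontinuation, and each leaver's number of pairs by setting (clinic or home). These counts show how far the repair can be trusted.
- **Fitting:** reconcile section 3.3.2 with sections 3.1.2 and 4.1.1 before deciding how people who do not tolerate the fitting are counted.
- **Optional:** one sensitivity analysis that sets leavers to the lowest observed participant mean. It is conservative: simulated rejection is 1.6%, 2.5% and 3.6% at slopes 0, 0.5 and 1.

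The cost is a few wording changes and no new data collection. Consent wording may also need to change; the consent pages were not available to check. The estimate may come out less favourable, and the repair stays partial if leavers contribute only the supervised Visit 1 pair.

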# 4.1.2 Between Visit (at home) phase

Patient wears collar for <4 hours total while awake for symptomatic relief as needed

Patient reports daily average tinnitus intensity with and without collar, length of use, and any adverse events through REDCAP email/text link

Continues daily for 14 days

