# 6.3.3 Safety Analysis

Adverse events are not expected; however, all subjects entered into the study at Visit 1 will be included in the safety analysis. The frequencies of AEs by type, body system, severity and relationship to study drug will be summarized if at all present. SAEs (if any) will be described in detail.

AE incidence will be summarized along with the corresponding exact binomial 95% twosided confidence intervals.

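### The primary analysis is called intention to treat but keeps only completers, and withdrawn subjects' ratings are deleted, so relief pairs from early leavers are lost and mean relief may be biased

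*Combined protocol and SAP*

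**What the plan says.** The primary population is set in one sentence of section 6.3.2: "The primary analysis will be based on an intention to treat approach and will include all subjects who complete the study". The same section plans 16 pairs per patient, one at each of two clinic visits and one on each of 14 home days, averaged and tested with a one-sided t-test.

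The first pair exists before the subject goes home. A baseline rating is taken, the collar is fitted, and then, under 3.1.2, "The patient will be monitored for 10 minutes for adverse effects, then asked to complete the scale once more". Home wear follows: "Patient wears collar for <4 hours total while awake for symptomatic relief as needed" (4.1.2).

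On leaving, 4.2 says "Subjects may withdraw from the study at any time without prejudice to their care", and 4.2.1 adds: "Subjects who withdraw from the study will have all records deleted from the REDCAP database except for adverse events". Section 4.2 also requires a record of whether each subject completes. Sections 3.1.4 and 3.2.1 place the end of participation at the Visit 2 exit surveys, on day 16.

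For safety the population is wider: "all subjects entered into the study at Visit 1 will be included in the safety analysis" (6.3.3). On numbers, 3.2.2 says: "It is expected that approximately 22 subjects will be enrolled to produce 20 evaluable subjects". Section 6 gives no missing-data method and no sensitivity analysis for early leavers.

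**The concern.** Even in a single-arm study, where intention to treat is used loosely, its plain meaning is everyone who started treatment. Restricting the set to completers contradicts that label, and the restriction is what would be applied.

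There is no parallel control group, so mean relief with the collar is the main efficacy result. Section 2 says the pilot data, if favourable, will support a multicenter grant application. A participant who gets little relief has less reason to continue. If such participants leave, the mean among those who remain is too favourable.

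The deletion rule matters as much as the population. Correcting 6.3.2 alone would not help, because withdrawn subjects' pairs would no longer exist for either a primary or a sensitivity analysis.

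**Working it through.** **Inputs**
- About 22 enrolled for 20 evaluable (3.2.2). The implied loss is 2/22 = 9.1%.
- 16 pairs per patient (6.3.2), which reproduces as 2 clinic + 14 home = 16.
- Effect on the 1-10 scale (6.4): 1 point in the text, 2 points in the substituted formula. Both are used below only to turn percentages into points.
- Leavers' relief and reasons for leaving are not in the documents, so they are assumed and varied.

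**Pairs at risk.** A fitted subject who leaves before Visit 2 holds the Visit 1 pair plus up to 14 home pairs, so 1 to 15. For two such leavers that is 2 to 30 of 22 × 16 = 352 planned pairs, at most 30/352 = 8.5%.

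**Effect on the mean.** Let N be the number fitted, k the number who leave, m the completers' mean relief, and f × m the leavers' mean relief.

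All-fitted mean = m(N − k + kf)/N

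Reported mean ÷ all-fitted mean = N/(N − k(1 − f))

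| Case | Calculation | Error in reported mean |
|---|---|---|
| Both losses are fitting failures (N = 20, k = 0) | 20/20 = 1.00 | 0% |
| N = 22, k = 2, f = 1 (relief equal to completers) | 22/22 = 1.00 | 0% |
| N = 22, k = 2, f = 0.5 | 22/21 = 1.048 | +5% |
| N = 22, k = 2, f = 0 | 22/20 = 1.10 | +10% |
| N = 22, k = 2, f = 1.5 (left despite good relief) | 22/23 = 0.957 | −4% |
| One fitting failure, one fitted leaver with f = 0 (N = 21, k = 1) | 21/20 = 1.05 | +5% |

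In points, for two fitted leavers with zero relief: 1 − 20/22 = 0.09 when m = 1, and 2 − 40/22 = 0.18 when m = 2.

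**What an all-fitted analysis would recover.** It uses the pairs actually given, not the leavers' underlying relief. If each of two leavers gave only a Visit 1 pair, and that pair equalled the completers' mean, the all-fitted mean is (20m + 2m)/22 = m and nothing moves.

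**Precision of a leaver's average.** If pairs are independent and equally variable, a one-pair average has √(16/1) = 4 times the error of a 16-pair average, and a two-pair average √(16/2) = 2.8 times.

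**The case against.** The best defence is that the effect is small and its direction is open. This is a pilot, and the zero-relief case moves the mean by 0.09 points at a 1-point effect. The two expected losses could be fitting failures: intolerance of the fitting is an exclusion in 3.3.2 that can appear only after consent, and the proposed set leaves those subjects out too. Participants might also leave with good relief because the collar was uncomfortable or embarrassing, which would bias the mean downward. All of this stands, and it limits the point to a conditional one.

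Four stronger readings are tempting but not supported.
- A reader might infer that completion is undefined. Sections 3.1.4 and 3.2.1 in effect define it.
- A reader might infer that nothing would be known about leavers. Completion status is documented (4.2), their adverse events are kept (4.2.1), and safety covers everyone entered. What is missing is their relief and any reason other than an adverse event.
- A reader might infer that low users will be removed, since 4.2 says "They may also be discontinued from the study at the discretion of the Investigator for lack of adherence to study treatment or visit schedules". But wear is as needed, the stated limits are ceilings (7.1.1), and no section makes low use a trigger for removal.
- A reader might infer a badly inflated false-positive rate. In a simulation with no true effect, where the two worst responders of 22 always leave, the one-sided 5% test rejects about 23% of the time. That rests wholly on the assumed pattern of leaving, for which the documents give no evidence.

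**Conclusion.** The point holds in conditional form. The contradiction in 6.3.2 and the deletion rule in 4.2.1 are plain on the text. Together they discard usable pairs from fitted subjects who leave before Visit 2 and rule out a full all-fitted sensitivity analysis.

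Whether this biases mean relief depends on who leaves and why, which the plan does not predict. On the protocol's own margin, the cases worked here run from 4% too low, through no error, to 10% too high. They assume that 22 is the number consented, that losses are either fitting failures or fitted early leavers, and that leavers' relief lies between zero and 1.5 times the completers'. The documents do not support saying that relief will be overstated, only that it could be and that the plan removes the means of checking. The correction is worth making because it is cheap and deleted data cannot be recovered.

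**What to change.** **Section 6.3.2.** Define the primary set as all subjects fitted with the collar at Visit 1 who give at least one with/without pair. Average the available pairs within each subject, give each subject equal weight, and report completers as a sensitivity analysis. Subjects who do not tolerate the fitting stay excluded under 3.3.2.

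**Section 4.2.1.** Keep data collected before withdrawal unless the participant asks for deletion. Report the number of early exits and the reasons.

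**Consent form.** Match the wording on data retention.

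The cost is a few wording edits, with no new visit or measure. Relabelling the analysis as completers-only would remove the contradiction but would not recover the data. The main downside is that early leavers may supply as little as one supervised clinic pair. Their averages would be noisier (about 4 times the error of a full 16-pair average if pairs are independent) and would reflect clinic rather than home relief. The change therefore reduces the possible bias without guaranteeing its removal, and the reported mean may be lower.

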# 2.2 Secondary Objectives (or Aim)

The secondary objectives are to:

- Determine if the collar effect varies with time
- Evaluate changes in quality of life as a result of collar use
- Compare home use with in clinic use

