# 3.2 Study Duration, Enrollment and Number of Sites

#### 3.2.1 Duration of Subject Study Participation

16 days: 1 day for consent, fitting, and initial evlauation; 14 days for at home use, and 1 day for follow up.

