#### 9.4.2 Risk Assessment

#### Not Greater than Minimal:

- Psychological
  - Wearing the collar might be embarrassing for some patients. This is averted through a flexible at home protocol in which they are only asked to wear the collar on an as needed basis for symptomatic relief and report their efficacy. Patients will be allowed to withdraw from the study at any time.
- Confidentiality
  - Any study has potential consequences a breach of confidentiality, this study will avoid those consequences through maintenance of the data in a password protected REDCAP database accessible only to the research team, all of whom are HIPAA certified.
- Discomfort
  - The device is FDA approved for contact sports, and there are no adverse risks for the indicated population. However there is a possibility that patients will feel discomfort when wearing it. Care will be made to ensure the fitting is optimize the patient's needs. Possibility of mild discomfort if collar used incorrectly; this will be averted by counseling patients to not use the collar while sleeping and by fitting the collar correctly to the neck circumference of the subject at the initial visit.

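### The time-effect ANOVA pools clinic days 1 and 16 with home days 2–15 and leaves its form unstated; read as a day-factor repeated-measures ANOVA, it counts any clinic/home difference as time

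*Combined protocol and SAP*

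**What the plan says.** Section 2.2 lists as a secondary objective: "Determine if the collar effect varies with time". Section 6.3.2 gives the test: "Subjects with and without collar scores will be averaged for each day of the study, ANOVA testing will evaluate for the presence"; what it looks for is an effect of time. The synopsis adds only that "ANOVA analysis of intensity differences will elucidate effect of time, if any".

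The days are of two kinds. Section 3.2.1 sets out "16 days: 1 day for consent, fitting, and initial evlauation; 14 days for at home use, and 1 day for follow up", and the schedule of procedures numbers them day 1, days 2–15 and day 16. At visit 1 the with-collar rating is a supervised reading: "The patient will be monitored for 10 minutes for adverse effects, then asked to complete the scale once more" (Section 3.1.2). Visit 2 is also supervised (Sections 3.1.4 and 4.1.3). At home the participant reports a daily average with and without the collar (Sections 3.1.3 and 4.1.2), and Section 9.4.2 says that "they are only asked to wear the collar on an as needed basis for symptomatic relief and report their efficacy".

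The plan treats a clinic/home difference as an open question with its own endpoint: "Supervised tinnitus intensity scale measurements will be compared to at home measurements to evaluate if perception of symptomatic intensity varies with environment" (Section 5.2.1). For this, Section 6.3.2 averages the relief at the two visits, to be "compared avross patients with the mean relief recorded during at home use using a bidirectional t test". It does not say whether that test is paired.

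No section takes the clinic days out of the time test, adds a setting term to it, names participant as a model term, or says whether day is a factor or a trend.

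**The concern.** A reading after a short supervised wear and a self-reported daily average may differ even if the collar works equally well throughout. If both kinds of day enter one time test with no term for setting, a stable clinic/home difference can be reported as a collar effect that changes over the study.

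The unstated form matters as much. Depending on how the ANOVA is run, the same sentence gives no test, a test with almost no power, or a test that absorbs setting. At stake is a stated secondary objective: the pilot could report a time effect that is really a setting difference, or miss real fading of relief.

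**Working it through.** **The plan's own count.** 2 clinic + 14 home = 16 pairs per participant, and 16 × 20 = 320, as in Sections 6.3.2 and 6.4. The plan gives no power figure for the time test.

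**Inputs.** From the documents: 20 participants, 16 days, SD 2 for each score (Section 6.4). Assumed: two-sided alpha 0.05 for this test (Section 6.4 sets 0.05 for the primary endpoint), the clinic/home gap in relief, the ICC of the daily differences, and the correlation r between the two ratings of a pair. The difference SD is √(2² + 2² − 2·r·2·2) = √(8 − 8r), which is 2.83 at r = 0 and 2.0 at r = 0.5. Noise is independent between days.

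**Readings with day as a factor.**
- *Daily means over participants.* Sixteen mean differences and 16 day levels leave no residual, so there is no F test.
- *Individual differences, no participant term.* Between-participant variance stays in the error. Simulated rejection is 0–1% with no gap and no trend. Power for a 1-point drift over days 1–16 is about 5% at ICC 0.5, SD 2. With a 1-point gap and no trend, rejection is 18/8/3% at ICC 0.3/0.5/0.7.
- *Repeated-measures ANOVA.* The clinic/home contrast is one of the 15 day degrees of freedom, so any gap adds to the time F statistic.

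**Size under the repeated-measures reading.** A step on 2 of 16 days has sum of squares gap² × 2 × 14/16 = 1.75 × gap². Hence λ = 20 × 1.75 × gap² / (SD² × (1 − ICC)), with 15 and 285 df. For a 1-point gap, SD 2 and ICC 0.5, λ = 35/(4 × 0.5) = 17.5, and the rejection probability is 73.9%. With no true trend:

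| Difference SD | Gap | ICC 0.3 | ICC 0.5 | ICC 0.7 |
|---|---|---|---|---|
| 2 | 0.5 | 14% | 19% | 31% |
| 2 | 1 | 55% | 74% | 95% |
| 2.83 | 0.5 | 9% | 11% | 16% |
| 2.83 | 1 | 27% | 38% | 64% |

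Simulation agrees. With a Greenhouse-Geisser correction at SD 2, the rates are about 6%, 9–10% and 17% for 0.5 point, and about 39/58/89% for 1 point.

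**Linear trend over 16 days.** Days 1 and 16 carry weights −7.5 and +7.5, so an equal gap cancels. Simulated rejection is about 5%.

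**Clinic/home t-test.** If paired, the variance per participant is SD²(1 − ICC)(1/2 + 1/14). At ICC 0.5, SD 2 this is 2 × 0.571 = 1.143, the SE is √(1.143/20) = 0.239, and power for 1 point is 98% (92/98/100% over the three ICCs). Unpaired it is 63/48/31%.

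**Home-day slope test.** The 14 home days have sum of squares 14 × (14² − 1)/12 = 227.5. A 1-point drift over days 1–16 is 1/15 = 0.0667 per day. At ICC 0.5, SD 2, with equal slopes in all participants and no missing days:
- Home days only: SE = √(2/227.5/20) = 0.0210, ratio 3.18, power about 85%. Type I error in simulation is close to 5%, whatever the gap.
- All 16 days with a clinic/home term (sum of squares 340): SE = √(2/340/20) = 0.0171, ratio 3.89, power about 96%.
- Home days, slopes varying with an assumed SD of 0.05 or 0.10 points/day: SE = √((2/227.5 + 0.05²)/20) = 0.0238 or, with 0.10², 0.0307; power about 75% or 54%.

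**The case against.** The strongest reply is that the documents say only ANOVA. A day-factor repeated-measures model is one reading, and silence about terms is not a decision to leave them out. This stands: a reader might infer that the plan is bound to report setting as time, and the documents do not support that. A linear trend over all 16 days would be unbiased by a gap that is the same at both visits.

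Second, a 1-point gap equals the whole minimum collar effect stated in Section 6.4, and nothing in the documents suggests a gap that large. At 0.5 point the artefact is modest, and with Greenhouse-Geisser at ICC 0.3 it is close to nominal. This also stands, so the 0.5-point row deserves as much weight as the 1-point row.

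Third, a reader might call a difference at visit 1 only a bias of the time test. Visit 2 is supervised too, so setting alone would not explain it. It may be real change since first use, which is what Section 2.2 asks about.

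Fourth, the plan has a separate clinic/home comparison and plots the submissions over time. If that comparison is paired, time would be declared without it being significant in under 1% of trials (1 point, SD 2); if unpaired, in 9/29/64%. This limits the risk of misreading, but it does not correct the time test, and the pairing is not stated.

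**Conclusion.** The point holds in a limited form. What is certain is that the time test takes in two kinds of measurement and that its unit, error term, form of day and handling of setting are unstated. With day as a factor, none of the three readings is sound.

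The false time effect is conditional on the repeated-measures reading and on a real clinic/home gap. Over the assumed values its probability runs from 9% to 31% for 0.5 point and from 27% to 95% for 1 point, uncorrected. The gap, ICC and difference SD are all assumptions.

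It would be wrong to infer that the efficacy conclusion is at risk: the primary test does not use this ANOVA. This is a lower-priority point on a secondary objective of a 20-person pilot, worth acting on because the remedy uses data already planned.

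**What to change.** In Section 6.3.2, and to match in the synopsis:

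- Analyse each participant's daily paired difference (no collar minus collar), and keep daily means for plots.
- Base the time test on home days 2–15: one slope per participant from days with both ratings, a one-sample t-test on the slopes, and the mean slope with a 95% CI. State a minimum number of days (for example 5) and report how many days have both ratings.
- Report the day 1 versus day 16 clinic change separately with a 95% CI, so that change since first use is not lost.
- State that the clinic/home t-test is paired within participant.

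An alternative is to keep all 16 days with participant, a clinic/home term and a prespecified form for day. This regains power but assumes the same gap at both visits.

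The cost is protocol wording and standard software, with no new data. Dropping the clinic days lowers power for a 1-point drift from about 96% to about 85% in the favourable case above, and further if slopes vary between participants. Missing days, foreseeable with as-needed wear, also cost power: with equal slopes, about 80% with 10% of home days missing at random and 66% with 30% (ICC 0.5, SD 2). A linear slope can miss non-linear change such as a plateau, so the daily plot should stay.
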